A scatter plot of Hgb values measured by Central Laboratory versus Hgb values measured by Hemocue will be produced along with Pearson's correlation coefficient. Regardless of visit and treatment group, all available pairs of Hgb (i.e. non-missing values in both from central laboratory and from the corresponding HemoCue measurement) will be used.

- **Dose adjustment**

The dose adjustment algorithm is described in Section 15.6.3, based on HemoCue Hgb values.

Dose at each assessment visit / final visit

Dose at each assessment visit and final visit will be summarized by treatment group using mean, standard deviation, minimum, P25, median, P75, mode, and maximum at each assessment visit. The final visit will be the last visit of treatment exposure for each subject. Mean dose during Week 40 to 52 will also be summarized and includes subjects who has at least one exposure record during Week 40 to 52. The summary will also be provided by Prior ESA use, prior ESA dose, prior ESA type, and ERI.

Duration (days) of treatment interruption due to Hgb >13.0 g/dL

The number and percentage of subjects who have a period of treatment interruption due to Hgb >13.0 g/dL will be summarized by treatment group. On subjects who have a period of treatment interruption due to Hgb >13.0 g/dL, the duration (in days) of treatment interruption due to Hgb >13.0 g/dL per subject will be summarized by treatment group using mean, standard deviation, minimum, P25, median, P75, and maximum. On-therapy Hgb values observed in scheduled visits will be counted in the summary. The summary will also be provided by prior ESA use.

Dose adjustment

The number and percentage of subjects with dose adjustments will be provided. Number of dose adjustments will be summarized by treatment group using mean, standard deviation, minimum, median, mode, and maximum. For dose adjustments frequency, the number and percentage of subjects will be provided by the number of dose adjustments (i.e. zero, one, two, three, four, ..., ten, eleven, and twelve or more; may be refined) by treatment group during the whole treatment period. For timing of dose adjustments, the

number and percentage of subjects with dose adjustments by each assessment visit will be provided by treatment group. The summary will also be provided by Prior ESA use.

Dose adjustment to reach the lower Hgb target (11.0 g/dL)

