7.4.2. Summary Measure

- **CKD progression (eGFR, serum creatinine, urine creatinine, urine albumin, urine albumin/creatinine ratio)**

Raw observed value at each assessment visits

The values will be summarized using mean, standard deviation, 95%CI, minimum, P25, median, P75, and maximum at each assessment visit by treatment group. Graphical summaries will be provided using mean and 95% CI over time.

Change from baseline at each assessment visit

The values will be summarized using mean, standard deviation, 95%CI, minimum, P25, median, P75, and maximum at each assessment visit by treatment group. Graphical summaries will be provided using mean and 95% CI over time.

Number (%) of subjects with eGFR decrease of 30% or more from baseline

The number and percentage of subjects with eGFR decrease of 30% or more from baseline will be summarized at each assessment visit by treatment group.

Number (%) of subjects with serum creatinine increase of more than double from baseline

The number and percentage of subjects with serum creatinine increase of more than double from baseline will be summarized at each assessment visit by treatment group.

- **Other**

Scatter plot of change from baseline in Hgb at Week 4 vs. covariates of interest

Scatter plot of change from baseline in Hgb at Week 4 versus following covariates of interest, body weight, baseline Hgb, prior ESA dose will be produced for the ITT and Efficacy PD populations. See Section 15.6.3 for the detailed derivations.

Scatter plot of mean dose during Week 40 to 52 vs. covariates of interest

Scatter plot of mean dose during Week 40 to 52 versus following covariates of interest, body weight, baseline Hgb, prior ESA dose will be produced for the ITT and Efficacy PD populations. See Section 15.6.3 for the detailed derivations.

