
 The following scatter plot figures will be produced for overall: 
 Mean Dose during Week 40 to 52 vs. Baseline Body Weight (kg) Mean Dose during Week 40 to 52 vs. Baseline Hgb Mean Dose during Week 40 to 52 vs. Prior ESA dose Different displays by prior ESA use will be used to differentiate them. Vertical axis will indicate the mean dose (mg), horizontal axis will indicate the covariates of interest; baseline body weight (kg), baseline Hgb (g/dL), or prior ESA dose (IU/week). Mean dose will be calculated from the arithmetic mean using the latest 3 exposure records (i.e., for completers Week 40, 44, and 48), which are based on the actual doses and the scheduled visits. Subjects who has less than 3 dosing records will be excluded from the figures. Mean dose during Week 40 to 52 will also be summarized and listed. Only individual plots will be provided unlike the scatter plot of Hgb assessments.

Time in Target Range																																			
Time (weeks and percentage) in Target Range During the Primary Efficacy Evaluation Period																																			

 For this reporting purpose, on-therapy Hgb values of central laboratory during Week 40 to Week 52, including unscheduled visits, will be used. However, if a central laboratory Hgb value is missing, a corresponding non-missing HemoCue Hgb value, which is associated with the identical subject number and visit, will be used. Number of days that a subject's Hgb is within the analysis range of 11.0-13.0 g/dL inclusive between Week 40 and 52, including any on-therapy Hgb values that were taken during this time period. Linear interpolation is used to estimate Hgb between visits, if a subject has an intermittent missing value (Rosendaal1993). 																																			
Illustration of calculation																																			

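### Section 15.6.3 builds the Week 40–52 mean dose from the last three exposure records even when they precede Week 40, and Section 7.3.2 uses a different inclusion rule for the variable of the same name

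*SAP*

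**What the plan says.** SAP Section 7.4.2 plans these plots for the ITT and Efficacy PD populations ("Scatter plot of mean dose during Week 40 to 52 versus following covariates of interest") and sends the reader to Section 15.6.3 for the derivation. There the variable carries the Week 40–52 label, for example "Mean Dose during Week 40 to 52 vs. Baseline Body Weight (kg". The rule is: "Mean dose will be calculated from the arithmetic mean using the latest 3 exposure records", with Weeks 40, 44 and 48 named for completers only. It uses actual doses at scheduled visits. The only exclusion is: "Subjects who has less than 3 dosing records will be excluded from the figures". The same block adds: "Mean dose during Week 40 to 52 will also be summarized and listed".

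Section 7.3.2, under the dose-by-visit summary, has a variable of the same name: "Mean dose during Week 40 to 52 will also be summarized and includes subjects who has at least one exposure record" in that period. It gives this inclusion rule but no formula.

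Under Section 4, both plot populations require only a baseline Hgb and one later scheduled Hgb, so subjects who stop treatment well before Week 40 belong to them.

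**The concern.** The label promises the dose given in the evaluation period, but the rule delivers the last three doses whenever they were given. The two coincide for completers. For others, some or all of the averaged doses can come from before Week 40, and nothing in Section 15.6.3 requires even one record at or after Week 40.

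Section 7.3.2 applies a window that Section 15.6.3 does not, and Section 15.6.3 says its variable also feeds a summary and a listing. A programmer following each section exactly would produce displays with the same label but different subjects and values. A reader of the plots of dose against body weight, baseline Hgb and prior ESA dose would take every point as a Week 40–52 dose, and some would not be.

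**Working it through.** The SAP gives no figure of its own to reproduce, so the check applies each rule to the visit schedule.

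**Inputs.** Scheduled dosing visits are Day 1 and Weeks 4, 8, …, 48, which is 1 + 12 = 13 visits (Section 15.2.1). Cohort 3 adds Week 2, giving 14. Assumptions: one exposure record per dosing visit, no gaps, and the Week 2 supply counts as a scheduled record.

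**Section 15.6.3 rule, by last dosing visit (13-visit schedule).**

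| Last dosing visit | Records averaged | Records in Weeks 40–52 |
|---|---|---|
| Day 1 or Week 4 | fewer than three, excluded | – |
| Week 8 | Day 1, Weeks 4, 8 | 0 of 3 |
| Week 12 | Weeks 4, 8, 12 | 0 of 3 |
| Weeks 16 to 36 | three latest, the last of them Week 36 at most | 0 of 3 |
| Week 40 | Weeks 32, 36, 40 | 1 of 3 |
| Week 44 | Weeks 36, 40, 44 | 2 of 3 |
| Week 48 | Weeks 40, 44, 48 | 3 of 3 |

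Of the 13 possible last visits, 2 give no value, 8 (Weeks 8 to 36) give a value with nothing in the window, 2 give a mixture and 1 lies fully inside: 2 + 8 + 2 + 1 = 13. With Week 2 in Cohort 3 the split is 2 + 9 + 2 + 1 = 14, because a subject last dosed at Week 4 then has three records (Day 1, Weeks 2 and 4). These are counts of possible last visits, not proportions of subjects.

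**The SAP's own dose illustration.** The dose-adjustment example in Section 15.6.3 has 4, 4, 2, 0, 0 and 1 mg at Day 1 and Weeks 4, 8, 12, 16 and 20. Counting 0 mg visits as records:

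- last record at Week 8: (4 + 4 + 2)/3 = 3.33 mg;
- last record at Week 20: (0 + 0 + 1)/3 = 0.33 mg.

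Either value would be plotted as a Week 40–52 dose although none of the averaged doses was given then. Under Section 7.3.2 this subject, if treatment ended there, has no record in the window and is left out.

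**Section 7.3.2 rule.** A subject last dosed at Week 36 or earlier is not included. Subjects last dosed at Week 40 or 44 are included. If the mean is taken over in-window records, as the label implies, they contribute one record (Week 40) or two (Weeks 40 and 44), whereas Section 15.6.3 fills up to three with Week 32 and 36 doses. Week 48 gives the same three records under both rules.

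**Comparison within the SAP.** Other Week 40–52 variables keep to the window. Time in target range leaves out subjects withdrawn before Week 40, the Quarter 4 oral iron dose is not generated for them (both Section 15.6.3), and Week 40–52 compliance uses only the Week 40 to 48 records (Section 15.6.2).

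**The case against.** The strongest defence is that the two rules serve different displays. The last-three rule stands under the scatter-plot heading and its exclusion is worded for the figures, while Section 7.3.2 governs the table. That has weight for the table: its inclusion rule ("includes subjects who has at least one exposure record during Week 40 to 52") keeps out anyone who stopped before Week 40. It does not rescue the figures, which would still plot out-of-window doses under a Week 40–52 label. The sentence extending the variable to a summary and listing also blurs the division.

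One could read the three-record minimum as three records within the window. That is not written, would leave the reference to completers with no purpose, and would still conflict with the one-record rule in Section 7.3.2.

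Several stronger inferences are tempting but not supported:

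- **The summary mean is contaminated by early doses.** The Section 7.3.2 inclusion rule prevents this for subjects who stopped before Week 40.
- **The stray points are titration doses pulled toward the starting dose.** Section 2.3 places daprodustat dosing from Week 4 to Week 52 under maintenance. On the 13-visit schedule only a subject last dosed at Week 8 brings in a Day 1 record; in Cohort 3, if Week 2 counts, only one last dosed at Week 4 does. The accurate description is doses outside Weeks 40–52.
- **Covariate relations are flattened.** No slope, correlation or test is planned for these plots. They show individual points only, unlike the central laboratory versus HemoCue plot.
- **A dose-adjustment endpoint is compromised.** The endpoints listed for that objective in Section 2.2 are dose-level distribution, interruption time and adjustment frequency, not this mean.

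**Conclusion.** The point holds as a wrong derivation rule and an internal inconsistency of limited consequence. Followed literally, Section 15.6.3 assigns a Week 40–52 mean dose to subjects with no dose in that period (last dosed at Week 8 to 36) and mixes periods for those last dosed at Week 40 or 44. Section 7.3.2 selects a different set of subjects for the same label.

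The reach is Figures 2.83–2.85 (ITT) and 2.89–2.91 (Efficacy PD), plus agreement with the descriptive dose summary and listing. No hypothesis test and no primary or principal secondary analysis is affected, and values for completers with all three records do not change. The share of points affected depends on how many subjects stop between their third record and Week 48. The SAP gives no such figure, so no percentage can be stated. The visit counts rest on the one-record-per-visit assumption. No dosing rule is in question.

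**What to change.** In Section 15.6.3, define the variable as the mean of actual doses at the Week 40, 44 and 48 records. Include subjects with at least one such record, as Section 7.3.2 does, and exclude those with none. State that this definition serves the table, the listing and the figures, and add the formula or a cross-reference in Section 7.3.2.

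The cost is a sentence or two of SAP text and one programming filter. The plots lose the subjects last dosed before Week 40, and some means will rest on one or two records, which gives up the three-record minimum now set for the figures.

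If the last three records are what the plots are meant to show, keep that rule but label the axis and titles *mean of last 3 doses*, and remove the sentence that ties it to the Week 40–52 summary and listing.

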
Overview of Study Design and Key Features	
	
 For ESA users, prior ESA will be replaced with epoetin beta pegol at the equivalent dose once every 4 weeks (Day 1). At Week 2, HemoCue Hgb value will be measured for subjects' safety confirmation. If the measurement shows an Hgb increase of >1.0 g/dL over 2 weeks, the dose of GSK1278863 will be reduced by one step (or treatment interrupted) at Week 4 (Cohort 3 only). 
Maintenance Dose
 
 Epoetin beta pegol will be administered once every 4 weeks from dosing interval change (once every 4 weeks) with Hgb \geq11.0 g/dL to Week 52 in ESA non-users and from Weeks 4 to 52 in ESA users Further details of dosing are provided in the protocol Section 6.4.
Time & Events	
 Refer to Appendix 2: Schedule of Activities
Treatment Assignment	
 The randomization schedule will be generated by GlaxoSmithKline (GSK) using the randomization system (Randall NG). In Cohort 1 and Cohort 3 (ND subjects), subjects will be stratified by the current ESA therapy (ESA non-user or ESA user) and the Hgb level on Day 1 and randomized in a 1:1 ratio to one of the two treatment groups according to the randomization schedule. In Cohort 2 (PD subjects), all eligible subjects will start treatment with GSK1278863 on Day 1.
Interim Analysis	
 No interim analysis is planned.

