The time (weeks and percent) within/above/below the target range will be summarized by treatment group using mean, standard deviation, minimum, P25, median, P75, and maximum. For the ITT population, the treatment differences (daprodustat – epoetin beta pegol) and the associated 95% CIs for the time (weeks and percentage) within the target range will also be provided. See Section 15.6.3 for details. The summary will also be provided by prior ESA use.

Time (in days) to reach the lower Hgb target (11.0 g/dL)

The time (days) to reach the lower Hgb target will be summarized by treatment group using P25, median, and P75 by Kaplan-Meier method. Kaplan-Meier plot of time to event will be provided using on-therapy Hgb values including unscheduled visits. Subjects who could not reach lower target will be regarded as censored. Subjects who have baseline central laboratory Hgb ≥ 11.0 g/dL will be excluded in this analysis. The summary will also be provided by prior ESA use.

Number (%) of subjects who have an Hgb level of less than 7.5 g/dL

The number and percentage of subjects who have an Hgb level of less than 7.5 g/dL during the treatment period will be summarized by treatment group. On-therapy Hgb values observed in both scheduled and unscheduled visits will be included in the summary.

Number (%) of subjects who have an Hgb increase of more than 2.0 g/dL over any 4 weeks

The number and percentage of subjects who have an Hgb increase of more than 2.0 g/dL over any 4 weeks (excluding Week 2) during the treatment period will be summarized by treatment group. For the ITT population, the odds ratio (daprodustat/epoetin beta pegol) will also be provided with its 95% CI. On-therapy Hgb values will be used for the summary. See Section 15.6.3 for details.

Number (%) of subjects who have an Hgb level of more than 13.0 g/dL and number of episodes

The number and percentage of subjects who have an Hgb level of more than 13.0 g/dL during the treatment period and number of episodes will be summarized by treatment group. On-therapy Hgb values observed in both scheduled and unscheduled visits will be included in the summary.

Scatter plot of Hgb assessments: Central Laboratory vs. HemoCue

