15.6. Appendix 6: Derived and Transformed Data

15.6.1. General

Multiple Measurements at One Analysis Time Point

 Subjects having both High and Low values for Normal Ranges at any post-baseline visit for safety parameters will be counted in both the High and Low categories of “Any visit post-baseline” row of related summary tables. This will also be applicable to relevant PCI summary tables. For multiple measurements at Screening and/or Day 1 visit, the screening pass visit record will be used for analysis (See Appendix 3: Assessment Windows)
Study Day

 Calculated as the number of days from Randomization Date: 
 Ref Date = Missing → Study Day = Missing Ref Date < Randomization Date → Study Day = Ref Date - Randomization Date Ref Date ≥ Randomization Date → Study Day = Ref Date - (Randomization Date) + 1
Unique Subject ID

 All subjects have unique subject ID for analyses even if a subject was enrolled after rescreened. Tables/figures/listings will be produced based on unique subject ID. For a rescreened subject, the unique subject ID will be derived from the first-assigned subject number though he or she seems to have different subject numbers in eCRF by screening assessments.
Rescreening Subjects

 For rescreened subjects, data collected in screening-pass visit will be used for analysis. They may have multiple records at Screening and/or Day 1 visit, which associates with a screening-pass visit and screening failure visit(s) Regarding a listing of SAEs in screening period, all pre-therapy SAEs captured in eCRF will be provided including screen failure records of rescreened subjects.
Treatment Start Date

 First randomized treatment start date
Treatment Stop Date - Daprodustat

 Calculated as the latest treatment stop date.
Treatment Stop Date – Epoetin Beta Pegol

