
 Following definition will be based on “assumed” treatment stop date because the treatment stop date is not captured in eCRF. 
Definition:
 
 If a subject has completed the treatment period (i.e., Week 52 visit record is present), treatment stop date will be calculated as Week 52 visit date.. 
 Week 52 visit date will be based on laboratory Hgb date. HemoCue Hgb date will be used when laboratory Hgb date is unavailable. If a subject has withdrawn from the treatment period (i.e., Week 52 visit record is missing), treatment stop date will be calculated as the latest dosing start date + XX days (1 day before the next treatment start date if a subject hadn’t withdrawn) 
 Subjects will have every 2 weeks or every 4 weeks injection of epoetin beta pegol, therefore assumed treatment stop date could include “+ 13 or 27 days” to mimic every 2 weeks or every 4 weeks dosing.

Subgroup definition
 
 For general considerations, see Section 5.4.2 Regarding prior ESA type, prior ESA dose, and ERI, see Section 15.6.2 Baseline iron use = use or non-use of pre-therapy iron medications (including ferric citrate (trade name Riona), see Section 15.6.3). History of diabetes will be derived from the current history diabetes (Yes/No) in medical history records. CKD stage will be derived from the eGFR measurement at a screening visit Cohort will be derived from the randomization number. 
 Cohort 1 = Randomization Number in PPD Cohort 2 = Randomization Number in PPD Cohort 3 = Randomization Number in PPD Dialysis will be derived from the randomization number. 
 ND subjects = Cohort 1 or 3 PD subjects = Cohort 2

Time Definitions (per GSK standard principles)
 
 1 week = 7 days 1 month = 30.4375 days 1 year = 365.25 days

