
NC: Not calculated, NA: Not available
 
 • Hgb laboratory assessment date will be used to calculate a duration (Ref Day) between assessments. 
 ○ Duration between assessments = [Hgb lab date] – [Hgb lab date of the previous measurement] 
If a subject has withdrawn from the treatment before Week 40 the duration between Week 40 to Week 52 cannot be calculated, the subject will not be included in a summary.
 
Basically, the duration should be [Week 52 lab date – Week 40 lab date] unless a subject has withdrawn before Week 52. In the case of withdraw before Week 52, Treatment Stop Date (see Section 15.6.1) will be used instead of Week 52.
 
 • As an above example, suppose a subject has Hgb reading 9.9 g/dL on August 1st (Week 40), then reading if 11.2 g/dL on September 1st. The assumption is made that the week, between these scheduled assessments the subjects Hgb increases from 9.9 to 11.2 g/dL in a linear manner, To following steps are taken to calculate the time (days) the subject’s Hgb was within target range (11.0 to 13.0 g/dL). 
 1. Calculate amount of Hgb shift (9.9 to 11.2 = 1.3 shift) and Hgb shift within range (0.2 out of shift is within range of 11.0 – 13.0) 2. Calculate percent of total shift (%) within range (0.2/1.3 = 15.38%) 3. Estimate the number of weeks since last visit within range (15.38% x duration between assessments = 15.38% x 31/7 weeks = 0.68 weeks within range) 
If a subject has an intermittent missing Hgb assessment (on-therapy), the linear interpolation will be done by ignoring missing Hgb data.
 
To calculate overall time (weeks) in Hgb target range, the total days in range for each time period are added together and divided by 7.
 
The % of time in range between Week 40 and Week 52 for a subject will be calculated by calculating overall time (weeks) within range and dividing by the total duration (weeks) between Week 40 to Week 52. Similarly, the % of time above Hgb target range and % of time above and below Hgb target range will be calculated,

Time (days) to reach the lower Hgb target (11.0 g/dL)

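### For subjects withdrawn in Weeks 40–52, percent time in range divides by a period that ends on a different date from the numerator, and that end date is defined differently in each arm

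*SAP*

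**What the plan says.** **Numerator.** SAP Section 15.6.3 (Time in Target Range) interpolates linearly between consecutive on-therapy Hgb values in Weeks 40 to 52, unscheduled visits included. The interval is defined as "Duration between assessments = [Hgb lab date] – [Hgb lab date of the previous measurement"]. No rule carries time past the last value.

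**Denominator.** The percent is obtained by "dividing by the total duration (weeks) between Week 40 to Week 52". For completers this is the Week 52 lab date minus the Week 40 lab date. For the others: "In the case of withdraw before Week 52, Treatment Stop Date (see Section 15.6.1) will be used instead of Week 52". Subjects withdrawn before Week 40 are left out.

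**Treatment Stop Date (Section 15.6.1).** For daprodustat: "Calculated as the latest treatment stop date". For epoetin beta pegol it is an assumed "treatment stop date because the treatment stop date is not captured in eCRF". Where there is no Week 52 record, "treatment stop date will be calculated as the latest dosing start date + XX days", the addition being 13 or 27 days for 2-weekly or 4-weekly dosing. Section 2.3 says "Epoetin beta pegol will be administered once every 4 weeks from dosing interval change", so 27 days is the usual case in this window.

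**On-therapy limit (Section 15.4.1.1).** Hgb counts as on-therapy up to Treatment Stop Date + 1 day in both arms.

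**Use (Section 7.3.2).** In the ITT population, treatment differences and "the associated 95% CIs for the time (weeks and percentage) within the target range will also be provided".

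**The concern.** A percent of time needs the same start and end for its numerator and its denominator. Here they share a start but not, for withdrawn subjects, an end. Days between the last Hgb and Treatment Stop Date are added to the denominator, yet they cannot be classed as within, above or below range. In effect they count against the subject.

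The length of that unclassified stretch is set by an arm-specific date convention: the last tablet in one arm, and a projected end of the dosing interval in the other. A between-arm difference with a confidence interval then partly reflects how stop dates are defined and not only how well Hgb was controlled.

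**Working it through.** **1. The plan's own example (Section 15.6.3).** Hgb 9.9 at day 0, 11.2 at day 31, 13.4 at day 92.
- In range: 31 × 0.2/1.3 + 61 × 1.8/2.2 = 4.77 + 49.91 = 54.68 days.
- 54.68/92 = 59.43% unrounded. With the plan's rounded 7.81 weeks, 7.81/(92/7) = 59.42%, the printed figure.

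The example reproduces. Its denominator ends at the last Hgb, so the mismatch does not show.

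**2. A withdrawn subject whose every Hgb is in range (a consistent rule would give 100%).** Let L be the days from Week 40 to the last on-therapy Hgb. Percent = L / (Treatment Stop Date − Week 40 date). Last injection on the day of the last Hgb:

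| Last Hgb and injection | Stop + 27 days | Stop + 13 days |
|---|---|---|
| Week 40 (L = 0) | 0/27 = 0% | 0/13 = 0% |
| Week 44 (L = 28) | 28/55 = 50.9% | 28/41 = 68.3% |
| Week 48 (L = 56) | 56/83 = 67.5% | 56/69 = 81.2% |

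Daprodustat, last Hgb at Week 44, last tablet 1, 7, 13.5 or 27 days later: 28/29 = 96.6%, 28/35 = 80.0%, 28/41.5 = 67.5%, 28/55 = 50.9%. Both arms lose, epoetin usually more.

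**3. Two cases that go the other way.**
- Epoetin, last injection at Week 40, subject leaves at the Week 44 visit. The assumed stop is day 27, and the day-28 Hgb is on-therapy under the + 1 day rule: 28/27 = 103.7%.
- Withdrawal Hgb 14 days after Week 44, last tablet on day 10. For daprodustat that Hgb is post-therapy: 28/38 = 73.7%. For epoetin, injected at Week 44, it is on-therapy: (28 + 14)/55 = 76.4%. Daprodustat is the lower arm.

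**4. Effect on the arm means.** The share withdrawing in the window is not in the SAP; I assume 5% (3–8%), equal in both arms. Further assumptions: all subjects in range, 4-weekly injections, last scheduled visit equally often Week 40, 44 or 48, departure evenly on days 0–27 after it, last tablet on the day of departure.

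*No withdrawal Hgb.*
- Epoetin loss per withdrawn subject: (27/27 + 27/55 + 27/83)/3 = (1 + 0.491 + 0.325)/3 = 60.5%.
- Daprodustat loss, averaging d/(L + d) over d = 0 to 27: (1 + 0.298 + 0.183)/3 = 49.4%.
- At 5%: 3.03 − 2.47 = 0.56 points net. At 3% and 8%: 0.34 and 0.89.

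*Withdrawal Hgb on the day of departure, on-therapy in both arms.*
- Epoetin loss, averaging (27 − d)/(L + 27): (0.500 + 0.245 + 0.163)/3 = 30.3%. Daprodustat loss: 0.
- At 5%: 1.5 points net. At 3% and 8%: 0.9 and 2.4.

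Which of the two applies is not settled. The schedule in Appendix 2 has hematology at early withdrawal, but Appendix 3 gives that visit no analysis time point.

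**The case against.** The strongest reply is that the denominator sentence is the same for both arms, few subjects are touched, and the stakes are low. Section 5.5 treats other secondary endpoints as complementary or exploratory, without multiplicity adjustment. Subjects withdrawn before Week 40 are already excluded, and time in range is also reported in weeks, where this denominator plays no part. All of that stands and limits the weight of the point.

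A reader might infer something stronger: that the rule is a fault of the epoetin arm alone and always lowers its result. The documents do not support that. Daprodustat also collects days without Hgb up to its last tablet, and step 3 gives one epoetin value pushed above 100% and one comparison in which daprodustat is lower. The longer assumed epoetin period also admits more late Hgb values into the numerator.

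A reader might also take the 3.0-point fall in the epoetin mean as the bias in the comparison. It is a one-arm loss. Daprodustat loses 2.5 points on the same assumptions, and subjects with only a Week 40 Hgb, who make up more than half of the 3.0, lose everything in both arms and add nothing to the difference.

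The reply does not remove the defect. A rule that scores an always-in-range subject 51%, or 104%, is wrong as written, whatever its average effect.

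**Conclusion.** The point holds as a definition error in the percent for subjects withdrawn between Weeks 40 and 52. The numerator ends at the last on-therapy Hgb and the denominator at Treatment Stop Date, which is recorded for daprodustat and assumed for epoetin. Individual percentages can be badly wrong. The net between-arm effect is small: about 0.6 points (0.3–0.9) without a withdrawal Hgb and about 1.5 points (0.9–2.4) with one that is on-therapy in both arms. Those figures rest on the assumed 5% (3–8%) withdrawal share and the other assumptions in step 4. The direction typically favours daprodustat but is not fixed. The rule should be corrected because it is cheap to do so and a between-arm interval is reported.

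**What to change.** In Section 15.6.3, for subjects withdrawn before Week 52:
- End the denominator at the last on-therapy Hgb used in the numerator, in both arms. Within, above and below then sum to 100%.
- Treat subjects with a single Hgb in the window as not evaluable for the percent, in both arms.
- State whether the early-withdrawal Hgb is used, with the same rule in both arms, and align Appendix 3 with that choice.

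Leave completers' denominators as they are. The cost is a short text change and a small programming change. The downside is that a few single-value subjects drop out of the percent summary.
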